1. To validate a predictive model based on baseline measures of biological and functional biomarkers. *Working hypothesis: Baseline factors that include functional and physiological status will predict clinically significant responses to therapy.* Change from use of end-effector and exoskeleton robots to solely exoskeleton will not significantly affect the prediction model. The rationale for the hypothesis is that the effects of assisted repetitive task practice is not dependent on a particular technology but does depend on a biological substrate. Expected outcomes: The predictive model will be externally validated, a receiver operating curve described, and the intervention and model validated on an exoskeleton platform for delivering therapy.

2. To identify the changes in the input and output of the affected primary motor cortex associated with change in motor impairment. *Working hypothesis: Increased input into the motor cortex, increased output from the motor cortex, or both, underlies the treatment effect of repetitive task practice.* Normalization (increase) in connectivity of affected primary motor cortex to other motor brain areas of both sides of the brain will be associated with reduction of motor impairment. In a subpopulation of treatment responders an increased effectiveness of the motor cortex in directly activating muscles will be demonstrated. Expected outcome: The causal role of task practice in changing a brain region's connectivity will be known, with potential uses as a surrogate measure of outcome in rehabilitation trials. Resting state BOLD MRI, transcranial magnetic stimulation, and clinical electrophysiology will be used to provide data regarding the mechanisms of training-related gains.

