The primary analysis will be correlation between change in physiological parameters (e.g. affected M1 connectivity, recruitment curve slope) and change in FMA. Analysis of H-reflex changes will be compared to recruitment curve changes to rule out a general change in lower motor neuron excitability. Secondly, there will be correlations of these parameters at baseline with baseline motor function measures. A more detailed analysis of the MRI data will also examine individual interregional connections to determine whether any of them are more sensitive to the intervention than others. There will be exploration of whether the predictive model also predicts changes in physiological measures, which could lead to more efficient studies in the future.

ID: Pro00003161

View: 5 Sub-Studies

- 1.0** *** Is there a sub-study or are there sub-studies associated with this study?**
There is no sub-study associated with this study.

ID: Pro00003161

View: 6 Study Population Summary

Study Population Summary

1.0 * What is the maximum number of subjects you plan to enroll at VAPHS?
80

2.0 * Do you plan on enrolling patients into different categories:
 Yes No

If yes, please explain:

3.0 If this is a multi-site study, indicate the projected total subject accrual:
70

4.0 * Please provide a justification for the sample size:

Based on our record of recruitment and design feasibility, we propose to enroll 64 participants. Our current 12-week study has an attrition rate after enrollment of 12% so we anticipate completing about 57. We verify that with our sample size of 57, we will be able to estimate the area under the Receiver operating characteristic (ROC) curve (AUC) with an adequate precision (that is, the standard error is reasonably small). The AUC is an important measure to describe the performance of a predictive model for a binary outcome such as the change in FMA of greater than 4. The table below displays the standard error (SE) of the estimated AUC for several values of the true AUC and different prevalence of responders [10]. The SE is less than 0.07 in all cases except when AUC is 0.7 and the proportion of responders is only 33%. (This is the current situation in the preliminary analysis, providing an upper bound on our AUC measure.)

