For Aim #2, which is based on correlations, a sample size of 57 would allow detection of Pearson correlations $r > 0.365$, which is comparable to individual correlations found in the Robot Biology study, assuming $\alpha = 0.05$, $\beta = 0.2$ [41]. This was confirmed by the Statistics Core using that data and PASS (v14.0) software.

ID: Pro00003161

View: 6.1 Study Population

Study Population**1.0 * Check all that apply to describe your study population:**

Study Population

 Non-Veterans Special Populations **Veterans** Vulnerable populations Other**2.0 * Indicate the inclusion criteria for enrollment:**

1. Clinically defined, unilateral, hemiparetic stroke with radiologic exclusion of other possible diagnosis
2. Stroke onset at least 6 months before enrollment
3. Present with Mild/Moderate to Severe arm dysfunction (based on Fugl-Meyer scores of 10 to 45)
4. Be medically stable to participate in the study
5. Be English speaking

3.0 * Indicate exclusion criteria for enrollment:

1. Unable to give informed consent
2. Have a serious complicating medical illness that would preclude participation.
3. Contractures, orthopedic problems, or other impairments that would interfere with the interventional training or limit the range of joint motion in the potential study arm
4. Visual loss such that the subject would not be able to see the test patterns on the robot computer monitor
5. Botulinum toxin to study arm within four months of baseline testing or if received during the study period
6. Unable to comply with requirements of the study
7. <21 years of age
8. Enrollment in another greater-than-minimal risk study
9. Presence of medical condition or implant that prevents safe administration of TMS (history of seizures, and/or currently taking any of the following medications: lamotrigine (Lamictal), levetiracetam (Keppra), oscarbazepine (Trileptal), topiramate (Topamax), phenytoin (Dilantin), carbamazepine (Tegretol), valproic acid (Depakote), phenobarbital (Barbita, Luminal, Solfoton) and/or metallic implant in the head and/or neck area including aneurysm clips or coils, stents, deep brain stimulators, electrodes, shrapnel/bullets, facial tattoos with metallic or magnetic-sensitive ink) or MRI. If participants have a medical condition or implant mentioned above, this only makes them ineligible for TMS and/or MRI, not for other parts of the study.
10. Pregnancy

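### Aim 2's primary correlation of change with change has no stated baseline adjustment, so baseline status cannot be excluded as a common cause

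*Combined protocol and SAP*

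**What the plan says.** View 4.1, item 1.0 (Analysis Plan for Aim #2) reads: "The primary analysis will be correlation between change in physiological parameters (e.g. affected M1 connectivity, recruitment curve slope) and change in FMA". No covariate, partial correlation or regression model is named. The same paragraph adds an H-reflex comparison directed at lower motor neuron excitability, secondary correlations of baseline physiology with baseline motor function, and a more detailed MRI analysis. It then says: "There will be exploration of whether the predictive model also predicts changes in physiological measures". None of these adjusts the primary correlation.

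View 6, item 4.0 sizes the aim as a simple correlation: "a sample size of 57 would allow detection of Pearson correlations" above 0.365, with alpha 0.05 and beta 0.2. The 57 are the completers expected from 64 enrolled.

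View 2, item 3.0 gives the Aim 1 working hypothesis: "Baseline factors that include functional and physiological status will predict clinically significant responses to therapy". Under Aim 2 the same item expects the causal role of practice in changing connectivity to become known, with possible use of the measure as a surrogate outcome.

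The design has one arm (View 1.5, item 4.0), and entry FMA runs from 10 to 45 (View 6.1, item 2.0). TMS and MRI are done at baseline and after final training in participants who have no exclusion for them (View 4, item 1.0).

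**The concern.** The plan contains both halves of a confounding path. Aim 1 asserts the first half, baseline status to FMA change. The Aim 2 exploration raises the second, baseline status to physiological change, as an open question. If both exist, the two change scores will correlate even when change in connectivity or recruitment slope has nothing to do with recovery. There is no control arm to help separate these explanations, and the range of entry severity is wide.

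At stake is the meaning of a positive result. The plan would read it as the mechanism of training-related gain and as a step towards a surrogate outcome. It could instead show only that people with a certain baseline change more on both measures. If baseline acts in opposite directions on the two changes, a real link could be masked. The baseline values needed to address this are already collected.

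**Working it through.** **Inputs from the documents:** n = 57 completers, r = 0.365, alpha 0.05, power 80% (View 6, item 4.0). Sidedness is not stated.

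**1. The plan's own figure.** By Fisher's z, n = ((1.960 + 0.842)/atanh(0.365))² + 3 = (2.802/0.3826)² + 3 = 56.6, so 57. The detectable r at n = 57 is tanh(2.802/√54) = 0.364. The stated figure reproduces as a two-sided test; one-sided would need only 46.

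**2. Precision cost of adjusting.** With k covariates the standard error of Fisher's z is 1/√(n − 3 − k). At n = 57 the detectable partial r is tanh(2.802/√53) = 0.367 with one covariate and tanh(2.802/√52) = 0.370 with two.

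**3. Size of the confounding, under assumptions.** Let b be the correlation of baseline with FMA change and a its correlation with physiological change. The documents give neither. For b, I assume 0.43. Under bivariate normality this corresponds to an AUC of 0.70 at 33% responders, a case named in the sample size section. For a, I take 0.2 to 0.5. With no direct link, the expected unadjusted r is a × b, and the two-sided rejection rate is Φ(√54·atanh(ab) − 1.960) + Φ(−√54·atanh(ab) − 1.960).

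| a | expected r = 0.43a | rejection rate |
|---|---|---|
| 0.2 | 0.086 | 10% |
| 0.3 | 0.129 | 16% |
| 0.4 | 0.172 | 25% |
| 0.5 | 0.215 | 36% (37% by simulation) |

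Over a wider grid, a = 0.2 with b = 0.3 gives 7%, and a = b = 0.5 gives 47%.

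**4. Effect on power.** First hold the direct link fixed at partial r = 0.365/√(1 − 0.43²) = 0.404. The unadjusted r is then ab + 0.404·√((1 − a²)(1 − b²)).

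| a | unadjusted r | power unadjusted | power adjusted (1 or 2 covariates) |
|---|---|---|---|
| −0.3 | 0.219 | 37% | 88% or 87% |
| 0 | 0.365 | 80% | 88% or 87% |
| +0.3 | 0.477 | 97% | 88% or 87% |

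Now suppose instead that the planning value of 0.365 is itself an unadjusted correlation. The partial r is (0.365 − ab)/√((1 − a²)(1 − b²)). With b = 0.43 and a = 0.2, 0.3 or 0.4, it is 0.315, 0.274 or 0.233. Power with two covariates is then about 65%, 53% or 40%.

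**5. Number with paired data.** Exclusion 9 (View 6.1, item 3.0) keeps people who cannot have TMS or MRI in the rest of the study, so fewer than 57 may contribute to Aim 2. The documents do not say how many. With two covariates, tanh(2.802/√(n − 5)) gives 0.395 at an assumed n of 50 and 0.441 at an assumed 40.

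**The case against.** The strongest reply is that confounding is possible here but not shown. No document gives a correlation between baseline and physiological change; the plan only proposes to look. The value of 0.43 describes the score of a whole model built from demographics, function, genomics, neurophysiology and neuroanatomy, so baseline FMA alone may carry less. This stands: the rejection rates in the working are illustrations.

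A reader might also infer that leaving out baseline simply wastes power. That does not hold in general. Power is lost when baseline relates mainly to FMA change, or to the two changes with opposite signs. When it drives both in the same direction, the unadjusted test rejects more often (97% against about 87% at a = +0.3).

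A reader might further infer that adjustment restores a 5% error rate at no cost. It does so only if the chosen covariates capture the whole confounder without measurement error. If 0.365 is an unadjusted value and same-direction confounding is real, the adjusted association is smaller and underpowered at this sample size.

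Finally, Aim 2 is the mechanistic aim. The study's primary purpose is the Aim 1 validation, which this point does not touch. The Aim 2 hypothesis about connectivity is worded as an association, which a correlation addresses directly. This limits the severity. It does not help the causal expectation in View 2, which baseline adjustment in a one-arm study would not justify either.

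**Conclusion.** The point holds as a gap in the primary Aim 2 analysis that should be fixed. The plan names no baseline adjustment, gives its own reasons to regard baseline status as a possible common cause, and intends a mechanistic reading. The silence also leaves the choice of adjustment open until the data are seen.

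Under assumed correlations of 0.43 and 0.2 to 0.5, the planned test would reject in about 10% to 37% of trials with no direct link. These rates assume normal variables, 57 complete pairs and a single confounder. The documents do not support a claim that the error rate is in fact inflated by that amount, or that the unadjusted analysis necessarily loses power.

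**What to change.** Pre-specify as the Aim 2 primary analysis a linear model of end-of-training FMA on change in the physiological measure, with baseline FMA and the baseline value of that measure as covariates. Report the partial correlation with its confidence interval, and keep the Pearson r alongside as descriptive. State that adjustment reduces confounding but does not remove it, and that it does not by itself support the causal wording under Aim 2 in View 2, item 3.0.

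Restate the detectable effect as a partial r for the number of participants who will actually have paired TMS or MRI data. It is 0.370 with two covariates only if all 57 do, and larger if fewer.

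The cost is a change of analysis wording, two degrees of freedom and no new data. The downside should be stated openly: if baseline drives both changes in the same direction, the adjusted association will be smaller than an unadjusted 0.365, and power will be below 80%.

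### Aim 2 hypothesises an increase in motor cortex input or output, but its primary change-change correlation cannot show that either one increased

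*Combined protocol and SAP*

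**What the plan says.** The hypothesis is in View 2, item 3.0, specific aim 2: "Increased input into the motor cortex, increased output from the motor cortex, or both, underlies the treatment effect of repetitive task practice". Two predictions follow. The first is "Normalization (increase) in connectivity of affected primary motor cortex to other motor brain areas of both sides of the brain", expected to go with reduced motor impairment. The second concerns output: "In a subpopulation of treatment responders an increased effectiveness of the motor cortex in directly activating muscles will be demonstrated".

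The part of View 4.1 that covers Aim 2 states: "The primary analysis will be correlation between change in physiological parameters". The other variable in that correlation is the FMA change; connectivity of the affected M1 and the slope of the recruitment curve are named as examples of the parameters. The same paragraph lists four further analyses:

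- an H-reflex control: "Analysis of H-reflex changes will be compared to recruitment curve changes to rule out a general change in lower motor neuron excitability";
- correlations at baseline between the physiological and motor measures;
- an MRI analysis that will "examine individual interregional connections to determine whether any of them are more sensitive to the intervention than others";
- an exploration of whether the predictive model also predicts physiological change.

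The sample size text (View 6, item 4.0) sizes Aim 2 for a correlation only: "a sample size of 57 would allow detection of Pearson correlations" above 0.365, with alpha 0.05 and beta 0.2.

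**The concern.** The hypothesis has two parts: the physiological measures increase, and that change goes with motor improvement. The primary statistic speaks only to the second part. A positive correlation can arise when mean connectivity or slope rose, when the mean did not move, or when it fell and participants with little motor gain fell further. Taken alone, it leaves the word increased unsupported.

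The prediction for responders is more exposed, because no analysis in this document is tied to it. The aim also proposes these measures as a possible surrogate outcome for later rehabilitation trials, so it matters whether they moved in the hypothesised direction as well as whether they covary with FMA.

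**Working it through.** **1. The plan's own figure.** Inputs from View 6, item 4.0: n = 57, alpha 0.05, beta 0.2, r = 0.365. Sidedness is not stated. By Fisher's z, N = ((z_alpha + z_power) / atanh(r))² + 3. Two-sided, this is ((1.960 + 0.842) / 0.3826)² + 3 = 56.6, so 57. The one-sided version gives 45.2 and does not match. The figure reproduces as a two-sided test; the sizing arithmetic is sound.

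**2. What the correlation cannot see.** Let x be the physiological change and y the FMA change. Then r = Σ(x − x̄)(y − ȳ) / √[Σ(x − x̄)² Σ(y − ȳ)²]. Replacing x by x + c moves x̄ by c and leaves every x − x̄ as it was, so r and its p-value do not change.

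**3. The same point on simulated data.** One set of 57 pairs of change scores, with x re-centred to three means:

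| Mean change in x | r (p) | One-sample t test of mean change, p | Share with an increase |
|---|---|---|---|
| +0.5 SD | 0.265 (0.046) | 0.0004 | 65% |
| 0 | 0.265 (0.046) | 1.00 | 53% |
| −0.5 SD | 0.265 (0.046) | 0.0004 (a fall) | 33% |

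**4. Responders can fall on average while r is positive.** Assume bivariate normal changes and responders as the top third on FMA change. The mean of the top third of a standard normal is 1.09. At r = 0.365, responders then average 0.365 × 1.09 = 0.40 SD above the group mean in x. If the group mean fell by 0.5 SD, responders would still have fallen by 0.10 SD, with the correlation at exactly the size the study is powered to detect.

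**5. The other Aim 2 analyses.** The H-reflex comparison uses recruitment curve change, and the interregional analysis implies looking at change over the intervention. Neither states an estimate, test or direction for the mean change in affected M1 connectivity or recruitment curve slope. The baseline correlations are cross-sectional, and the predictive-model exploration is again an association.

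**6. What an estimate of mean change could detect.** Noncentral t, 80% power, two-sided 0.05, in SDs of the change score. The responder share is 33% in View 6, item 4.0 (0.33 × 57 ≈ 19) and about half in View 2, item 3.0 (28 of 57).

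| Contrast | n | Detectable |
|---|---|---|
| Mean change, all | 57 | 0.38 SD |
| Mean change, responders | 28 | 0.55 SD |
| Mean change, responders | 19 | 0.68 SD |
| Responders v non-responders | 28 v 29 | 0.76 SD |
| Responders v non-responders | 19 v 38 | 0.80 SD |

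Participants who cannot have TMS or MRI may stay in the study (View 6.1, exclusion 9), and their number is not given. If 50, 45 or 40 had data (assumed values), the overall figure would be 0.40, 0.43 or 0.45 SD.

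**The case against.** The strongest reply is that the aim is worded as identifying changes associated with change in impairment, and that a change-change correlation is the natural analysis for that. This stands. The correlation tests the association, and its sign shows whether larger physiological gains go with larger motor gains. A reader might infer that the primary analysis misses the aim altogether; the documents do not support that. It is silent only on whether the measures rose.

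A reader might also infer that nothing planned looks at pre-post change. That too goes beyond the text: the H-reflex comparison and the interregional analysis both come near it, and View 2 speaks of quantifying changes in connectivity. What is missing is a stated estimate of mean change.

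A third inference would be that the investigators will read a positive correlation as an increase. The plan contains no such rule. The most that can be said is that it leaves that reading open.

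Two further points have weight. The document is a submission form that lists a separately uploaded grant application (View 1.3), so the absence is an absence from this document only. The responder prediction refers to a subpopulation of responders. If that means a subset of them, a mean over all responders is not an exact match, and the wording needs to be settled.

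**Conclusion.** The concern holds in a limited form. As written, the Aim 2 primary analysis can support covariation between physiological and motor change, but cannot by itself support increased input or output, and no estimate of mean change is stated elsewhere in the document. The invariance in step 2 is algebra and rests on no assumption, except that the change scores vary: flat here means zero mean change, since r is undefined with no variation at all.

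The responder figures of 0.68 and 0.80 SD should not be taken as best cases. They use the lower of the two responder shares in the document; with about half responding they are 0.55 and 0.76 SD. All the detectable sizes assume that every one of the 57 completers has usable data, and they get larger if not.

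Aim 1 and the sample size arithmetic are unaffected. This should be changed, but it does not put the study as a whole in doubt.

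**What to change.** In the Aim 2 analysis plan, keep the correlation and add:

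- The mean change from baseline to post-training, with 95% confidence interval, for affected M1 connectivity and for recruitment curve slope, in all participants with data and in responders (FMA change greater than 4). Give the responder minus non-responder difference as supportive.
- A reporting rule: input or output is described as increased only when the confidence interval for the relevant mean change lies above zero. Otherwise a positive correlation is reported as covariation only. A positive point estimate is not enough, since it would occur about half the time with no true change.
- A statement that the study has one arm (View 1.5, item 4.0), so a mean rise shows change over time and not a causal effect of practice.
- A definition of the responder subpopulation to which the output prediction applies.

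Two measures by three contrasts make six added estimates. Label them as supporting estimates or adjust for multiplicity.

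The cost is analysis wording only, because View 4 already schedules TMS and MRI at baseline and after final training for participants without exclusions. The downside is that the claim becomes harder to meet and the responder intervals will be wide.

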*** Does this research study involve any of the following:**

Name

- Deception
- Interview/Focus Groups
- Use of Drug, biological, or nutritional (e.g., herbal or dietary) supplement (investigational or FDA approved)?
- Use of medical devices**
- Prospective Analysis of Specimens
- Banking of Specimens-Data
- Retrospective use of specimens
- Audio/Video Recordings or Photographs
- Honest Broker or other similar service
- None of the Above

ID: Pro00003161

View: 3.4 Use of Medical Devices

Medical Devices

1.0 * Specify all devices used on this study:

Device Name	Manufacturer	Use of Device	IDE Number (if Applicable)	Device Brochure	Description of Use	Risk Level Determined by Sponsor
The MagStim 200	MagStim	FDA Approved but used in unapproved way				Non-Significant Risk

2.0 * Describe your plan for storage and control of devices:

The device will be stored in a secure laboratory environment only accessible by research study staff. Use is restricted to individuals who have been educated and trained.

ID: Pro00003161

View: 4 Research study methods

Research Study Methods

Describe all study related procedures following enrollment of a subject in this study.

Please see Section 6 for where the study team defines when a subject will be considered enrolled in the study.

1.0

* Research Procedures/Interventions:

After obtaining informed consent and a review of medical records, participants will be seen for a neurological exam visit by the PI and initiation of study evaluations.

All baseline testing will occur within a 6 week time frame and will include 2 separate baseline functional upper extremity outcome evaluations and one baseline robot evaluation with the rehabilitation robots in measurement mode for quantitative measures of upper extremity kinematics and strength. If participants have differences in Fugl-Meyer scores greater than 2, one additional baseline may be administered to establish the more stable result with only two baseline datasets used for analysis. On all participants who do not have any TMS or MRI medical exclusion criteria one baseline TMS evaluation and one baseline MRI will occur.

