After completion of the baseline evaluations, the intervention phase of the study will begin. During this time, participants will complete a total of 36 intervention sessions of Robot +TTT training. These will occur 3 times per week for 12 weeks. If scheduling conflicts arise, changes will be allowed with sessions occurring up to 4 times per week but will not exceed 18 total weeks. The intervention sessions will be one hour in duration. During each session, participants will complete 45 minutes of robotic intervention followed by 15 minutes of TTT. Participants will progress through 3 robot programs sequentially with 12 sessions focused on distal upper extremity function, 12 sessions focused on proximal upper extremity function and the final 12 sessions alternating between a distal and proximal focus. Functional outcome and robot evaluations will occur after each robot block, at final training, and at a 12 week retention follow-up. On all participants who do not have any TMS or MRI exclusion criteria one TMS evaluation and one MRI will occur after final training. Also, one TMS evaluation and one MRI will occur at the 12 week retention follow-up. The retention follow-up visit must occur within 4 weeks of when it is due. All procedures are routinely done within clinical practice.

Baseline/Outcome evaluations:

Upper extremity measures and evaluations will consist of: the Fugl-Meyer Upper Extremity Motor Assessment (FMA), the Wolf Motor Function Test (WMFT), Stroke Impact Scale (SIS), Action Research Arm Test, isometric strength and range of motion evaluations of the shoulder, wrist, thumb, and grip. The *Activity Monitor* wearing schedule will occur at baseline (3 days), and post-training.

The Fugl-Meyer Upper Extremity Motor Performance Section Test:

Selected because it assesses impairments and has been shown to be valid and has high inter-rater reliability and test/retest reliability [46]. In particular, it correlates well with interjoint coordination measures in the UE of stroke patients [47]. The Fugl-Meyer [48] has been shown to be both internally and externally valid. According to Duncan et al., it is probably the most widely known scale of motor recovery after stroke and can be considered a *gold standard* for motor impairment measures [49] but its relationship to task performance is not clear. It is a primary outcome variable because it measures impairment and we can compare it to other studies.

The Wolf Motor Function Test:

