A high resolution MPRAGE (TE 3.44 ms, TR 2250 ms, T1 900 ms, flip angle 9°, 1.5 mm isotropic voxels) will be obtained. Two resting state BOLD (T2*) scans will be obtained, with TE=30 ms, TR = 2000 ms, FOV=220mm, resolution=64X64 with 36 4 mm axial slices over 10 min to yield 380 volumes each. Diffusion tensor images for fractional isotropy (FA) analysis will be obtained using the most up to date Siemens protocols to maximize resolution and will be optimized for determination of FA rather than tractography. An ROI and seed based method will be used to determine the FA value for the posterior limb of the internal capsule on each side and a voxel-based correlation of a seed in the arm area of the primary motor cortex with the rest of the brain. A Z transformed score for mean correlation of the seed ROI with the rest of the brain will be obtained and will serve as a variable for the prediction model. This will also lead to an exploration of the relationship of this connectivity measure with lesion and function. Volumetric data will be normalized and right hemisphere strokes mirrored so that all images are in the same space, with the affected hemisphere on the left. But the ROI and seed-based approaches will be carried out in individuals to avoid most of the blurring effects of normalization. The spatial normalization itself will be purely linear affine transformations, with masking of large lesions to reduce normalization error. An atlas-based approach to the internal capsule and primary motor cortex UE representation will be used (e.g. WFU Pick-atlas, Maldjian et al., 2003, NeuroImage 19, 1233 9.) In general we will use a combination of

public domain tools for image analysis, include AFNI, SPM, FSL, and MRICron, all listed at <http://www.nitrc.org>.

INTERVENTION (Robot + TTT)

All participants will be enrolled in the same intervention: Robot + TTT. The intervention proposed will be completed 3x/week for 12 weeks. The training progression will be sequential with 12 sessions focused on distal upper extremity function, 12 sessions focused on proximal upper extremity function and the final 12 sessions alternating between a distal and proximal focus. Participants will perform robot training on an FDA-approved robot for 45 minutes followed by 15 minutes of TTT practice to complete their 60 minute intervention session.

Transition to Task Training (TTT):

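### Aim 2's detectable correlation of 0.365 assumes all 57 completers have paired MRI or TMS data, although the protocol enrols people who cannot have those tests

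*Combined protocol and SAP*

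**What the plan says.** - **Planning figure.** Study Population Summary (View 6), item 4.0: "For Aim #2, which is based on correlations, a sample size of 57 would allow detection of Pearson correlations" above 0.365, with alpha 0.05 and beta 0.2. The text adds that the Statistics Core confirmed this with PASS.
- **Origin of the 57.** The same item proposes 64 participants and notes that the current 12-week study "has an attrition rate after enrollment of 12% so we anticipate completing about 57". No other loss is deducted.
- **Analysis being powered.** Analysis Plan for Aim #2 (View 4.1): "The primary analysis will be correlation between change in physiological parameters (e.g. affected M1 connectivity, recruitment curve slope) and change in FMA".
- **Who may enrol without the tests.** Study Population (View 6.1), exclusion criterion 9, lists seizure history, named medications and "metallic implant in the head and/or neck area including aneurysm clips or coils, stents", among other items. It then says of a listed condition that "this only makes them ineligible for TMS and/or MRI, not for other parts of the study".
- **Who is tested.** Research Study Methods (View 4), item 1.0, at baseline: "On all participants who do not have any TMS or MRI medical exclusion criteria one baseline TMS evaluation and one baseline MRI will occur". After training: "On all participants who do not have any TMS or MRI exclusion criteria one TMS evaluation and one MRI will occur after final training".
- **Other enrolment figures.** View 6 also gives a VAPHS maximum of 80 and a projected multi-site accrual of 70.

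**The concern.** A change score needs the same measurement at two times. Someone barred from MRI has no connectivity change, and someone barred from TMS has no recruitment-slope change. Under criterion 9 both can still enrol, train, complete and be counted among the 57. The number that matters for each Aim 2 correlation is the number of completers with paired data in that modality, and the plan does not state it.

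This is the only power statement for Aim 2. It does not distinguish modalities, so a reader will take 0.365 as the sensitivity of both the MRI and the TMS correlation. If some completers are barred, a null result in the affected modality would be read against a sensitivity the design did not have.

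**Working it through.** **Inputs from the documents:** n = 57, r = 0.365, alpha 0.05, power 80%, enrolment 64, attrition 12% (View 6, item 4.0). Sidedness is not stated.

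**Input not in the documents:** the share *s* of completers barred from a given modality. Assumed values: 5%, 10% and 20%.

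**Step 1: reproduce the plan's figure.** Fisher z, two-sided: r_min = tanh[(1.960 + 0.842)/√(n − 3)]. At n = 57 this is tanh(2.802/√54) = tanh(0.381) = 0.364. In reverse, r = 0.365 needs n = (2.802/atanh 0.365)² + 3 = 56.6, rounded up to 57. A one-sided test would give 0.326 at n = 57, which does not match, so the plan evidently used a two-sided test. Its arithmetic is correct for 57 complete pairs.

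**Step 2: check the attrition step.** 64 × 0.88 = 56.3, which the plan rounds to about 57. Nothing is left over to absorb missing MRI or TMS data.

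**Step 3: deduct barred completers.** Paired n = 57 × (1 − s), rounded down: 57 × 0.95 = 54.15, 57 × 0.90 = 51.3, 57 × 0.80 = 45.6. Power at r = 0.365 is approximately Φ[atanh(0.365) × √(n − 3) − 1.960]. The last column simulates the t-test for r with 200,000 bivariate normal samples.

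| Barred share (assumed) | Paired n | Detectable r, 80% power | Power at 0.365, Fisher z | Power at 0.365, simulated t-test |
|---|---|---|---|---|
| 0% | 57 | 0.364 | 80.3% | 81.0% |
| 5% | 54 | 0.373 | 78.0% | 78.9% |
| 10% | 51 | 0.384 | 75.5% | 76.4% |
| 20% | 45 | 0.407 | 69.8% | 70.8% |

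Rounding 45.6 up to 46 gives 0.403 and 70.9% by Fisher z.

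**Step 4: enrolment needed for 57 pairs in one modality.** N = 57/[0.88 × (1 − s)]:

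- 5%: 57/0.836 = 68.2, so 69
- 10%: 57/0.792 = 71.97, so 72
- 20%: 57/0.704 = 80.97, so 81

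**Step 5: compare with the three enrolment figures.** The largest barred share that still leaves 57 pairs is 1 − 57/(0.88 × N).

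- 64 covers none of the assumed shares.
- 70 leaves 61.6 completers and covers up to about 7.5%.
- 80 leaves 70.4 completers and covers up to about 19%.

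The justification rests on 64 and does not use 70 or 80.

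**The case against.** The strongest reply is that the size of the problem is assumed. No passage gives a barred share or says that anyone in the preceding study was barred. At 5% the detectable r moves only from 0.364 to 0.373. On the simulated t-test, 56 pairs still give 80.2% power, and power first drops below 80% at 55 pairs (79.5%). The plan calls 0.365 only comparable to earlier correlations, and because those values are not shown, 0.37 to 0.41 might be comparable too. All of this stands, and it limits the weight of the point.

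The loss may also be uneven. Much of criterion 9 concerns TMS safety, so the MRI correlation could lose few people. That is fair, and it is why a figure per modality is needed. Overlap is possible in the other direction: the TMS Outcomes text in View 4 builds the neuronavigation from the participant's MRI.

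Recruiting to 70 or 80 would give real room, as Step 5 shows, but the plan does not make that argument. Nor can the 12% attrition be read as covering the loss, because criterion 9 keeps barred people in the study. The PASS confirmation supports the arithmetic, but the text does not say it addressed how many paired records to expect. The grant application, which is not among the documents reviewed, may do so.

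Finally, no success or futility rule depends on 0.365, and a null correlation can be read from its interval at the actual n. That reduces the harm but does not make the stated n right.

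**Conclusion.** The concern holds. The detectable correlation is computed correctly for 57 pairs, but the protocol's own eligibility and testing rules do not deliver 57 pairs in every modality once any completer is barred, and nothing is deducted for this.

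Over an assumed barred share of 5% to 20%, the detectable r rises to about 0.37 to 0.41, and power at 0.365 falls to between 78% and 70%. These figures assume a two-sided 0.05 test, approximately bivariate normal data, 57 completers, and no paired data lost for other reasons. The true share is unknown and the effect may be small. The omission is certain; its size is not.

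The conclusion concerns the Aim 2 planning statement only. View 4 says the MRI connectivity score "will be obtained and will serve as a variable for the prediction model", so barred participants may also lack an Aim 1 predictor. That was not assessed here.

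**What to change.** In View 6, item 4.0, replace the single Aim 2 sentence with one statement for the MRI connectivity correlation and one for the TMS recruitment-slope correlation. Each should give:

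- the expected number of completers with paired baseline and post-training data, using the ineligible fraction seen in the preceding study or, failing that, a stated range such as 5% to 20%;
- the correlation detectable with 80% power at that number, noting that the test is two-sided.

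Also say whether the calculation rests on 64, 70 or 80 enrolled.

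The cost is a rewording and a look at the preceding study's records. It needs no added enrolment and no change to conduct or analysis. The only downside is a slightly less favourable stated figure, about 0.37 to 0.41 over the assumed range instead of 0.365.
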